We will exclude patients with no intraoperative anesthetic records. Cardiac surgery patients (identified by procedure anatomy “Heart” or “Cardiac” within Innovian) are excluded since they have a unique set of considerations and complications due to having surgery directly in the heart. To include the full spectrum of non-cardiac surgical patients, no specific surgeries will be excluded except for deceased organ donation (“organ retrieval” in Innovian procedure name, and American Society of Anesthesiologists classification for neurologically-deceased organ donors, ASA=VI).

Preliminary analysis of our intraoperative database estimates approximately 35,000 patients in this cohort. For patients with multiple procedures, the date of the first surgical procedure with an overnight stay will be used to identify the specific surgical admission of interest.

Data Sources

The de-identified dataset will consist of databases from Innovian, Horizon Surgical Manager (HSM), and Health Data Nova Scotia (HDNS). Innovian is the intraoperative anesthesia electronic information management system used at the QEII, containing automated recordings of intraoperative standard monitors, time-stamped anesthesiology entries of medications and interventions, and perioperative laboratory tests. HSM contains vital signs and administrative data at the anesthetic preoperative clinic, in the preoperative area prior to the surgery, and in the recovery room after surgery.

The specific HDNS databases to which access is being requested are the Canadian Institute for Health Information (CIHI) Discharge Abstract Database (DAD) and Vital Statistics. DAD is a repository of clinical and administrative data from each hospitalization, including preoperative diagnoses, surgery performed, postoperative complications, and investigations.

DAD includes the 25 most relevant diagnoses preoperatively and postoperatively. Nova Scotia physician billings data will not provide any additional relevant information and are not necessary for this project. The Vital Statistics database records all deaths within Nova Scotia. Innovian and HSM data will be linked together by health card number and surgical date by the Innovian Data Manager (Innovian-HSM dataset). The health card numbers will be sent to Medavie for encryption. HDNS will link the Innovian-HSM dataset with the HDNS variables by encrypted study IDs and surgery date. National and provincial privacy and data security policies will be strictly followed.

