Heart rate	Since both fast and slow heart rate may be harmful and there is no universal definition of abnormal heart rate under anesthesia, we will model using a variety of methods. 
 1. Maximum change (BPM) from preoperative heart rate (positive and negative) 2. Relative change (%) from preoperative heart rate (positive and negative) 3. Maximum pulse variation (maximum heart rate minus minimum heart rate) 4. Longest single episode (minutes) a) below 60, and b) above 100BPM 5. Cumulative duration (minutes) a) below 60, and b) above 100BPM
Use of hemodynamic medications (i.e. special medications for blood pressure)	
 1. Vasopressor/inotrope use (yes vs. no): phenylephrine, norepinephrine, epinephrine, vasopressin, dobutamine, or milrinone 2. Infusion of any vasopressor/inotropes above (yes vs. no) (identified by unit of weight over time) 3. Phenylephrine/ephedrine bolus (yes vs. no) (identified by unit of weight only) 4. Vasodilator use (yes vs. no): labetalol, esmolol, nitroglycerin, nitroprusside 5. Infusion of any vasodilator above (yes vs. no) (identified by unit of weight over time)
Oxygen saturation by pulse oximetry: SpO₂	
 1. Longest single episode (minutes) below a) 88, and b) 90% 2. Cumulative duration (minutes) below a) 88, and b) 90%
End-tidal (i.e. exhaled) Carbon dioxide: EtCO₂	
 1. Longest single episode (minutes) a) below 30, and b) above 45mmHg 2. Cumulative duration (minutes) a) below 30, and b) above 45mmHg

II. Outcomes

Primary: 30-day all-cause postoperative mortality (binary)

Secondary:

1. Major 30-day in-hospital morbidity, both in terms of the individual category (yes/no), and an overall composite (i.e. yes for any of the 6 categories vs. no). We have included major morbidity outcomes where increased monitoring would be beneficial, using International Statistical Classification of Diseases (ICD) 10 codes and based on published protocol on patient safety indicators (27).
 1. Cardiac: composite of acute myocardial infarction, cardiac arrest, ventricular tachycardia, congestive heart failure, pulmonary edema, complete heart block, shock excluding septic shock
 2. Respiratory: composite of pneumonia, pulmonary embolism, acute respiratory failure, respiratory arrest, Mechanical Ventilation \geq 96 hours
 3. Acute Kidney Injury
 4. Cerebrovascular: composite of strokes and transient ischemic attacks

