CIHI DAD	PATIENT_ID: encrypted health card number For HDNS internal use	Patient	Jan 1, 2013 to Dec 1, 2017	HDNS data linkage with Innovian-HSM. The dataset given to us will not contain Patient_ID, but rather a Study ID.
Vital Statistics	PATIENT_ID: encrypted health card number For HDNS internal use	Patient	Jan 1, 2013 to Dec 1, 2017	HDNS data linkage with Vital Statistics. The dataset given to us will not contain Patient_ID, but rather a Study ID.
CIHI DAD	PDATE[1-n]: procedure date	Patient	Jan 1, 2013 to Dec 1, 2017	HDNS data linkage with Innovian surgery date, to ensure that only the admission corresponding to the surgery admission of interest (first surgery admission with LOS>1) is included.

				
The PDATE matching the date of procedure (+/- 1 day) from Innovian will be used. The corresponding number (e.g. PDATE1) will be used for all procedure-related codes (e.g. PCODE1, PDSERV1).
 
Note that except for preoperative comorbidity data, where we would need data for 3 years prior to PDATE, for all other variables we only need data within 30 days after PDATE.

CIHI DAD	
LOS: Length of Stay (after surgery)
 
Derived by HDNS: discharge date minus PDATE + 1 (includes day of surgery)
	Patient	
Jan 1, 2013 to Dec 1, 2018 (to account for prolonged LOS postop from the end of inclusion date)
	
Part of inclusion criteria: if a patient had multiple surgeries, the first surgery with a LOS >1 (i.e. at least overnight stay). To calculate ratio of LOS to Expected Length of Stay (ELOS) as secondary outcome. We have chosen to standardize LOS to only include duration of stay after surgery, since there are many factors that may prolong a patient's stay prior to surgery.

Additional Demographic Information				
CIHI DAD	SEX: Patient sex	Patient	
Jan 1, 2013 to Dec 1, 2017
	
As sex may affect outcomes, this will be included as a covariate in our models
 
M = Male
 
F = Female

HSM	BMI: Body Mass Index [Derived by Innovian]	Patient	
Jan 1, 2010 to Dec 1, 2017
	
Dichotomized according to WHO definition for obesity: BMI>30. This will be combined with ICD code to create a binary Obesity variable (please see below).

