CIHI-DAD	Admit-date	Patient	1Jan2010 to 31Dec2017	
For 3-year look-back window with: either admission date or discharge date is between surgery date (B) and 3 years before B (A), assuming that A<B.
 
For 30-day follow-up window with: Either admission date or discharge date is between surgery date (B) and 30 days after B (C), assuming that B<C.

CIHI-DAD	Discharge_date	Patient	1Jan2010 to 31Dec2017	For 3-year look-back window with: either admission date or discharge date is between surgery date (B) and 3 years before B (A), assuming that A<B.

				For 30-day follow-up window with: Either admission date or discharge date is between surgery date (B) and 30 days after B (C), assuming that B<C.
CIHI DAD	ECI: Elixhauser comorbidity index [Derived by HDNS]	Patient	Jan 1, 2010 to Dec 1, 2017 (3 years before and including date of surgery)	
To be computed by the HDNS according to protocol (32) using DXCODES (please see above), to be included into model as covariate. Please report both total score, and any of the following individual categories:
 
Congestive heart failure Cardiac arrhythmias Valvular disease Pulmonary circulation disorders Peripheral vascular disorders Hypertension, uncomplicated Hypertension, complicated Paralysis Other neurological disorders Chronic pulmonary disease Diabetes, uncomplicated Diabetes, complicated Hypothyroidism Renal failure Liver disease Peptic Ulcer Disease Excluding Bleeding AIDS/HIV Lymphoma Metastatic cancer Solid tumor without metastasis Rheumatoid arthritis/ collagen vascular diseases Coagulopathy Obesity Weight loss Fluid and electrolyte disorders Blood loss anemia Deficiency anemia Alcohol abuse Drug abuse Psychoses

				Depression

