CIHI DAD	FLAG_HE_ARTRESUS : Heart Resuscitation Flag	Patient	Jan 1, 2013 to Dec 31, 2017	Part of secondary outcomes to be included into model. Descriptive statistics will be performed for this subcategory, within the category of cardiac complications, and an overall composite measure of each category. 0 = No 1 = Yes
CIHI DAD	FLAG_ME_CHVEN_G_E96: Mechanical Ventilation \geq 96 hours	Patient	Jan 1, 2013 to Dec 31, 2017	Part of secondary outcomes to be included into model. Descriptive statistics will be performed for this subcategory, within the category of respiratory complications, and an overall composite measure of each category. 0 = No 1 = Yes
CIHI DAD	Composite morbidity [Derived by HDNS]	Patient	Jan 1, 2013 to Dec 31, 2017	Binary variable (yes/no) derived based on any of the following: FLAG_HEARTRESUS, FLAG_MECHVEN_GE96, or ICD code of any of: acute myocardial infarction (I21 to I22, I24), cardiac arrest (I46.0, I46.1, I46.9), ventricular tachycardia (I47.2), shock (R57, T81.1) excluding septic shock (R57.2), congestive heart failure (I50.0, I50.1, I50.9), pulmonary edema (J81), complete heart block (I44.2), pneumonia (J13 to J18, J69.0, J69.8, J95.4), pulmonary embolism (I26), acute respiratory failure (J95.1, J95.2, J96.0), respiratory arrest (R9.2), strokes and transient ischemic attacks (I60 to I69),

				
G45), Delirium (F05), Acute kidney injury (N17), Septic shock (R57.2)
 
Part of secondary outcomes to be included into model. Descriptive statistics will be performed.

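### Major morbidity counts the resuscitation and ventilation flags without an operational rule that the event followed surgery, and the individual delirium outcome is coded F5 in one row but F05 elsewhere

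*Combined protocol and SAP*

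**What the plan says.** Under II. Outcomes, major morbidity is analysed as six separate categories and as an any-of-six composite. The respiratory category is a composite of "pneumonia, pulmonary embolism, acute respiratory failure, respiratory arrest, Mechanical Ventilation" for 96 hours or more.

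Appendix 1 gives the derivation:

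- **Flags.** The row for "FLAG_HE_ARTRESUS : Heart Resuscitation Flag" and the row for the ventilation flag each give only 0 = No, 1 = Yes, with a calendar span from January 2013 to December 2017. For the ventilation flag the plan adds: "Descriptive statistics will be performed for this subcategory, within the category of respiratory complications, and an overall composite measure of each category". The resuscitation flag has the matching sentence for cardiac complications.
- **Composite.** The Composite morbidity row is positive for any of "FLAG_HEARTRESUS, FLAG_MECHVEN_GE96, or ICD code of any of" the listed conditions, including "Delirium (F05), Acute kidney injury (N17), Septic shock (R57.2").
- **Time window.** The PDATE row says that, preoperative comorbidity apart, "for all other variables we only need data within 30 days after PDATE". The Admit-date and Discharge_date rows put the follow-up window into operation: "Either admission date or discharge date is between surgery date (B) and 30 days after B (C), assuming that B<C".
- **Delirium.** The postoperative-outcome list in the DXCODE row, which is said to feed the individual, category and composite outcomes, gives delirium as F5. The UCAUSE, All causes of death and Composite morbidity rows give F05.

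**The concern.** The secondary hypothesis links intraoperative pressure, heart rate, saturation, end-tidal carbon dioxide and hemodynamic medication to 30-day major in-hospital morbidity. A patient resuscitated, or ventilated for several days, earlier in the same admission is likely to come to surgery unstable and to show exactly those exposures. If that earlier event is then scored as a postoperative complication, the outcome precedes the exposure. The error would not be random: it would gather in the most unstable patients and would tend to inflate the association under test.

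The delirium mismatch is a separate matter. Delirium is one of the six categories analysed on its own, and the DXCODE row is the only place where that individual outcome is given a code. Health Data Nova Scotia (HDNS) derives the outcomes from this appendix, so a wrong code there is a wrong extraction instruction.

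**Working it through.** The plan states no figure for this point, so there is none to reproduce. The check is a comparison of rules, a code match and an illustration of size.

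**1. Timing rules side by side (Appendix 1)**

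| Outcome element | Rule tying it to surgery |
|---|---|
| ICD-coded complications (DXCODE row) | Types 2 and 3 count unless prefix 5 (arose before the intervention); type M counts only with prefix 6 (during or after) |
| ICU admission | SCU admit date compared with PDATE |
| Length of stay | Counted from PDATE |
| Readmission | Within 30 days of PDATE |
| Heart-resuscitation flag | None beyond the general 30-day statement |
| Ventilation flag | None beyond the general 30-day statement |

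**2. Does the general statement close the gap?** It says which data are wanted. The rule that applies it works on admission and discharge dates. Take an admission that began before surgery and ended within 30 days after it. It enters through its discharge date, with whatever flags it carries. Neither flag row asks for an event date, so nothing in the derivation separates an event before PDATE from one after it.

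**3. Are the flags admission-level?** The documents do not say so directly. Data Sources says "DAD is a repository of clinical and administrative data from each hospitalization", and the window in step 2 selects whole admissions. The flag rows list the level as Patient, but that column records level of identification and is not a time rule. Admission-level is therefore an inference, though nothing in the documents contradicts it.

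**4. Delirium code.** F5 was matched against F00 to F99:

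- as an exact code it matches nothing;
- as a prefix it matches F50 to F59;
- neither reading returns F05.

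Read literally, the individual delirium category holds no F05 case, while the Composite morbidity row counts them all.

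**5. Size of the flag problem (illustration only).** The documents give N of about 35,000. They give neither the share q of patients whose flag comes from a preoperative event nor the true composite rate m. Assume q = 0.1% to 1% and m = 5% to 15%, and let flagged patients have the same true morbidity as the rest.

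False positives: FP = N × q × (1 − m). Share of composite positives: FP / (FP + N × m).

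- Low: 35,000 × 0.001 × 0.85 = 29.75; 29.75 / (29.75 + 5,250) = 0.6%.
- Middle (q = 0.5%, m = 10%): 35,000 × 0.005 × 0.90 = 157.5; 157.5 / (157.5 + 3,500) = 4.3%.
- High: 35,000 × 0.01 × 0.95 = 332.5; 332.5 / (332.5 + 1,750) = 16.0%.

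Patients this ill probably have more genuine postoperative complications than average. They would then be composite-positive anyway, so these counts lean high.

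**The case against.** The strongest reply is that the plan does tie these fields to surgery. The PDATE row limits all non-comorbidity data to the 30 days afterwards, the flags sit under a heading for additional postoperative morbidity, and the outcome is named as 30-day in-hospital morbidity. This shows the intent clearly, and a reader should not infer that the plan overlooked timing. It does not supply a method for an undated 0/1 field.

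Other parts of the reply stand:

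- How the flags are populated is not documented. In particular, nothing supports the inference that a resuscitation in the emergency department before admission would set the flag.
- Preoperative ICU admission and emergency surgery are candidate covariates (Table 2), so part of any distortion would be adjusted away if they are retained.
- The Composite morbidity row already uses F05. A reader might infer that the composite loses delirium too, but that follows only if it is built from the DXCODE list instead.
- F5 is very likely a typing slip beside a plain-language label, and the planned descriptive statistics might expose an implausible count. Even so, it stands in the extraction specification.

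Two further readings are tempting but not supported. The resuscitation flag does not appear in the cardiac definition under II. Outcomes. However, the Appendix is where variables are detailed, it places the flag among cardiac complications, and cardiac arrest is already listed in the main text, so this is summary against detail. A cardiac arrest code printed in some rows with a digit 1 where the letter I is expected may come from reading the PDF and is not counted as a defect.

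**Conclusion.** The concern holds in a limited form. As written, the derivation can count a resuscitation or prolonged ventilation earlier in the index admission as a postoperative cardiac or respiratory event and as a composite event. This rests on the inference that the flags describe the whole admission. It reaches only patients with such an event earlier in the same stay; their number is not given and is probably small, and the 0.6% to 16% range is wholly a product of assumed rates. The documents do not show that such miscounting will occur, only that no rule prevents it.

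The F5/F05 disagreement is a definite inconsistency between rows. Followed literally, it would empty the individual delirium category of its intended cases and make that category disagree with the composite row.

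Both problems concern secondary outcome 1. The primary outcome, 30-day mortality, comes from Vital Statistics and is not touched.

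**What to change.** 1. In both flag rows and the Composite morbidity row, have HDNS count a flag only when the event can be dated on or after PDATE. State which date applies to ventilation that spans surgery.
2. Where the events cannot be dated, make the ICD-based composite, which already carries onset markers, the main definition, and report the composite with the flags as a sensitivity analysis. Align the respiratory definition under II. Outcomes with whichever choice is made. Removing flags only for patients already in ICU before surgery is not a good substitute: it would discard genuine postoperative events in the patients at highest risk and would miss earlier events outside ICU.
3. Change F5 to F05 in the DXCODE row, and use one checked code list in the DXCODE, UCAUSE, All causes of death and Composite morbidity rows. Include respiratory arrest in that check: R9.2 is printed consistently in all four rows, but it has one digit before the point where the other codes, F5 apart, have two.

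The cost is some appendix wording, a small change to the HDNS derivation code and possibly a slightly lower morbidity count. Under the fallback, flagged events with no qualifying ICD code leave the main composite; the sensitivity analysis would show how many.

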The results of this study may help synthesize complex intraoperative clinical information and unveil novel therapeutic strategies. Derived from data from the QEII Hospitals, the results would be directly applicable to the care of Nova Scotians. The models may lead to the creation of objective risk stratification scores calculated at the end of surgery, to identify high risk patients for increased postoperative follow-up and monitoring. Moreover, if models created using machine learning perform well, machine learning may be used more frequently to reveal the patterns within complex, large perioperative datasets. Hemodynamics are potentially modifiable risk factors. Future research includes prospective studies on whether targeted hemodynamic goals, increased postoperative follow-up of high-risk patients, and real-time machine learning precision medicine could improve outcomes after surgeries.

Specific aims

1. To use machine learning techniques to investigate systematically intraoperative hemodynamic predictors of postoperative 30-day all-cause mortality (primary outcome) and major in-hospital morbidity. Hemodynamic predictors to be studied are blood pressure, heart rate, oxygen saturation, end-tidal carbon dioxide, and medications to adjust blood pressure. Please see “Outcomes” section below for full list of secondary outcomes.
2. To evaluate performance of machine learning models created and compare the performance of the best model to the Surgical Apgar Score.

Hypothesis

Controlling for other predictors, the durations of mean arterial pressure (MAP) <65mmHg, heart rate <60 or >100 beats per minute (BPM), hemodynamic medications use, oxygen saturation (SpO₂) <88%, and end-tidal carbon dioxide (EtCO₂) <30 or >45 will be associated with postoperative 30-day all-cause mortality (primary hypothesis) and 30-day major in-hospital morbidity (secondary hypothesis). Note that blood pressure, heart rate, vasopressors and

inotropic medications, oxygen saturation, and end-tidal are considered key indicators of hemodynamics. We have chosen conventional ranges commonly used in practice, and will perform sensitivity analysis of different definitions of each hemodynamic variable.

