 5. Delirium
 6. Septic Shock
2. Postoperative ICU admission (yes/no)
3. Prolonged Postoperative Length of Stay (LOS) (greater than vs. less than or equal to CIHI Expected Length of Stay (ELOS) as assigned by the Case Mix Grouping) [note that the LOS includes the day of surgery]
4. Hospital readmission within 30 days (yes/no)
5. Intraoperative mortality (yes/no)
6. Days alive and out of hospital at 30 days postoperatively (28)

III. Other predictors included into model

The following potential perioperative predictors will be evaluated as covariates during model building. Statistically significant predictors will be retained in the model.

Table 2. Other predictors

Preoperative	
 1. Demographics: age on date of surgery, sex, obesity (body mass index>30) 2. Indicators of preoperative comorbidities: since no comorbidity score has perfect performance, a variety of models will be evaluated and the most significant predictive score will be retained in the model. 
 • American Society of Anesthesiologist class • RCRI score(29), and specific components via ICD codes (history of ischemic heart disease, congestive heart failure, cerebrovascular disease, diabetes, chronic kidney disease, and CCI and Case Mix Group codes of suprainguinal vascular, intraperitoneal, or intrathoracic surgery) using previously published methods (30)(31) • Elixhauser comorbidity index (32) and Charlson Comorbidity Index (33): calculated using diagnoses from the previous three years according to standard algorithm by HDNS. Reported as both total score and individual categories • Hospital Frailty Risk Score (34): based on ICD codes • Preoperative blood pressure: ICD diagnosis of hypertension and by measured blood pressure • Preoperative heart rate: Innovian and HSM • Chronic Obstructive Lung Disease (ICD code): since it may affect the interpretation of results of SpO₂ and EtCO₂ 3. Indicators of surgical complexity 
 • CIHI DAD Case Mix Group (CMG) class (also contains categories that include medical complexity) • Main Surgical Service • Procedural Index for Mortality Risk (PIMR) (35): according to CCI • Procedure: CCI codes • Preoperative ICU admission • Emergency surgery: as determined by DAD Method of Entry = emergency department or transferred from another institution)

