The performance of all models created will be evaluated in the validation set as part of internal validation using the same metrics of discrimination, calibration, and risk reclassification, and compared to the Surgical Apgar Score. Since there will likely be significant class imbalance and ROC curves may overestimate model performance, for each model, precision and recall curves (PRC), F score, average precision, and AUC will also be reported and compared. The best performing model will also be used to analyze for predictors for secondary outcomes. Sensitivity (recall, true positive rate), specificity, positive predictive value (precision), G-mean, negative predictive values, False Discovery Rates (FDR), optimism, and measures of association of hemodynamic thresholds for primary and secondary outcomes will be computed. Bayesian network causal inference analysis may be performed, to help increase interpretability.

Sensitivity and subgroup analysis

Sensitivity analysis will be performed for different definitions of hemodynamic derangements. Subgroup analysis will be performed based on age, sex, high preoperative risk (most significant indicator of preoperative comorbidity in Table 2, based on final model), RCRI, frailty (HFRS), preoperative hypertension, a select list of intermediate-high risk, gender-neutral elective surgery (please see Appendix – RCRI Protocol Table 1), emergency surgery, and type of anesthesia.

Power calculation

The 2016-2017 in-hospital mortality after major surgery in Nova Scotia is 1.7% (47). Using the Events Per Variable criterion (EPV) of at least 10 outcomes per predictor in the sample, the 1.7% mortality (408) out of an estimated sample size of 24,000 for the derivation/training group means that our model would be valid for up to 41 predictors for the primary outcome. However, the EPV may over or underestimate the limitations of the EPV criterion (48), square root of the mean squared prediction error (rMPSE) and mean absolute prediction error (MAPE) will be calculated based on the number of predictors, sample size and events fraction (49) with the caveat that this model has not been externally validated. Full power calculation will be performed once we receive the final sample size.

Strengths

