CIHI DAD	
ICU admission [Derived by HDNS]
 
SCUNUM[1-n]: Special Care Unit Num “The SCU Unit Number is a code identifying the type of special care unit where the patient receives critical care.”
 
[Derived by HDNS]
	Patient	
Jan 1, 2013 to Dec 31, 2017
	
Two variables to be derived:
 
 1. Preoperative ICU (yes/no) 2. Postoperative ICU (yes/no) 
Preoperative ICU admission (yes/no) is a covariate to be included into the model. Postoperative ICU admission (yes/no) is a secondary outcome to be included into model. Descriptive statistics will be performed.
 
Derivation process: ICU = yes include the following SCUNUM: 10 = Medical Intensive Care Nursing Unit 20 = Surgical Intensive Care Nursing Unit 25 = Trauma Intensive Care Nursing Unit 30 = Combined Medical/Surgical Intensive Care Nursing Unit 35 = Burn Intensive Care Nursing Unit 40 = Cardiac Intensive Care Nursing Unit Surgery 45 = Coronary Intensive Care Nursing Unit 80 = Respirology Intensive Care Nursing Unit Else ICU = no
 
If the SCU Admit Date is on or before PDATE, then it would be defined as Preoperative AND postoperative ICU admission. Else, postoperative ICU admission only.

CIHI DAD	READMIT: Readmission Code (within 30 days after PDATE) [Derived by HDNS]	Patient	Jan 1, 2013 to Dec 31, 2017	
Readmission within 30 days of PDATE (yes/no) is a secondary outcome to be included into model. Descriptive statistics will be performed.
 
Derived: Postoperative readmission = yes include the following:
 
 1 = Planned readmission from previous acute care 2 = Unplanned readmission within 7 days following discharge from acute care 3 = Unplanned readmission 8 – 28 days following discharge from acute care 4 = ≤ 7 days, unplanned 5 = New patient 9 = None of the above. 
Else Postoperative readmission = no

CIHI DAD	LOS:EOS Ratio of Length of Stay (LOS) to Expected Length of Stay (EOS) as assigned by the Case Mix Grouping [Derived by HDNS]	Patient	Jan 1, 2013 to Dec 31, 2017	
This will be dichotomized by HDNS: LOS:EOS > 1 (yes/no). This is a secondary outcome to be included into model. Descriptive statistics will be performed.

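### The ICU rule compares dates only: ICU admissions after surgery on the day of surgery become a preoperative covariate, and every patient so flagged counts as a postoperative ICU event

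*Combined protocol and SAP*

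**What the plan says.** In Appendix 1, the ICU admission row asks the data custodian to derive two yes/no variables from the special care unit (SCU) admission date and the procedure date (PDATE). The first branch reads "If the SCU Admit Date is on or before PDATE, then it would be defined as Preoperative AND postoperative ICU admission". The second covers all other ICU patients: "Else, postoperative ICU admission only". The row names no admission time, end-of-surgery time or SCU discharge date, and no other section refines the rule.

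The two variables have different roles. The same row states that "Preoperative ICU admission (yes/no) is a covariate to be included into the model", and Table 2 lists "Preoperative ICU admission" in its preoperative block. Postoperative ICU admission is a secondary outcome. The text above Table 2 adds that "Statistically significant predictors will be retained in the model".

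Three other places bear on the consequences. The primary hypothesis is an adjusted association: "Controlling for other predictors, the durations of mean arterial pressure (MAP) <65mmHg" and the other listed exposures are to be related to 30-day mortality. Under Evaluating model performance, "The best performing model will also be used to analyze for predictors for secondary outcomes". Under Data linkage, Step 2, the Innovian surgery date is the reference date, and PDATE may differ from it by up to 1 day.

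**The concern.** A date cannot tell an ICU admission before surgery from one after surgery on the same day. The rule places both in the preoperative group, so the covariate mixes a baseline risk marker with an early postoperative event. That event follows the intraoperative blood pressure, heart rate and oxygenation under study and may result from them. Adjusting for it could remove part of the association that the primary hypothesis is about.

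The rule also makes the outcome follow from the covariate. Everyone flagged preoperative is a postoperative ICU case, including a patient discharged from ICU before surgery who went to a ward afterwards.

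Aim 2 compares the best model with the Surgical Apgar Score, which is fixed at the end of surgery. A same-day ICU admission after surgery has not yet happened at that point. The temporal validation set would not expose the problem, because it uses the same derived variable.

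**Working it through.** **The plan's own figures.** No figure in the plan depends on the ICU rule. The one borrowed here is the derivation sample in the Power calculation, "an estimated sample size of 24,000 for the derivation/training group". The arithmetic around it reproduces: 24,000 × 0.017 = 408 deaths, and 408 / 10 = 40.8, the plan's 41 predictors. It supplies only the denominator below.

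**Step 1: the rule as logic.** Let day 0 be PDATE. Preoperative = yes if any SCU admission falls on day 0 or earlier. Postoperative = yes if there is any ICU stay at all. Pairs are (preoperative, postoperative), with 1 = yes.

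| Patient | True pair | Coded pair |
|---|---|---|
| No ICU stay | (0,0) | (0,0) |
| ICU from day −2, back to ICU after surgery | (1,1) | (1,1) |
| ICU on day 0 before surgery, returns there | (1,1) | (1,1) |
| ICU on day 0 straight from the operating room | (0,1) | **(1,1)** |
| First ICU stay on day +1 | (0,1) | (0,1) |
| ICU from day −5, left before surgery, ward afterwards | (1,0) | **(1,1)** |

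The two errors differ. In the day-0 case the outcome is right and the covariate is wrong. In the last row the covariate is right and the outcome is wrong.

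**Step 2: which pairs can occur.** Enumerating every set of 0 to 3 ICU stays with admission days from −5 to +5 gives only (0,0), (0,1) and (1,1). The pair (1,0) never occurs, so P(postoperative ICU = yes | preoperative = yes) = 1 whatever the data.

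**Step 3: the choice of date.** The rule uses PDATE, not the Innovian date. If PDATE is recorded one day late, an ICU admission on the day after the true surgery date is also flagged preoperative. If PDATE is one day early, all day-of-surgery admissions become postoperative only, which is right for those after surgery and wrong for those before it. The documents do not say how often the dates differ.

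**Step 4: size.** The documents give neither the same-day postoperative ICU rate nor the rate of ICU care before surgery. Per 1% of patients admitted to ICU after surgery on the same day:

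- derivation set: 0.01 × 24,000 = 240 patients wrongly flagged;
- estimated full cohort: 0.01 × 35,000 = 350 patients.

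The 6.7% in the Introduction is unplanned ICU admission in an American cohort. It gives no same-day share, so it does not yield an estimate for this cohort.

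**Step 5: a related timing point.** Table 2 lists hemoglobin as intraoperative but takes the lowest value from the day of surgery to 2 days afterwards, and Appendix 1 agrees. Appendix 1 also describes Case Mix Group, another covariate, as a grouping that draws on length of stay and resource use. Neither is fully known at the end of surgery.

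**The case against.** The joint coding looks deliberate. With only an admission date named, treating a patient already in ICU as also a postoperative ICU patient is a workable convention, and many such patients will return there. This stands for patients who do return. It does not cover those who left ICU before surgery, and it does not justify calling an admission after surgery preoperative.

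The harm to the mortality model is conditional. Appendix 1 says the covariate goes in, but the text above Table 2 keeps only significant predictors. This stands: the effect depends on retention, and its direction and size are unknown. A reader might infer that the primary result is biased by a material amount; the documents do not support that.

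A reader might also infer that the postoperative ICU model cannot be fitted because the flag determines the outcome. That goes too far. Creating the models names LASSO and Elastic Net, which are penalised; the plain logistic regression after the second PCA is for the primary outcome; and it is not stated whether the covariate set or only the technique carries over to secondary outcomes. What remains is that, if the flag is carried over, part of its apparent predictive strength comes from the coding.

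The 1-day difference is a maximum tolerance, and the Innovian date is already the reference. That makes Step 3 a minor addition.

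The hemoglobin window is openly stated and listed under bleeding, and an end-of-surgery score is only something the models may lead to. It is therefore a timing note, not an error. Restricting the window could also raise missingness towards the 20% at which the Missing data section removes a variable.

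**Conclusion.** The point holds for the ICU derivation. Followed as written, the plan gives a wrong covariate value to each patient whose first ICU admission is after surgery on the day of surgery, and a false outcome event to each patient who left ICU before surgery and did not return. Both follow from the text without assumptions. The size does not: 240 derivation patients per 1% is a scale, not an estimate, and the number who left ICU before surgery is also unknown.

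The consequences are conditional. The mortality model is affected if the flag is retained, and the postoperative ICU model if the flag is carried into it. The primary outcome's definition is untouched, and same-day postoperative admissions are still counted in the secondary outcome. This should be fixed before the variables are derived. Hemoglobin and Case Mix Group call only for an additional run of the Surgical Apgar comparison; correcting the ICU flag alone would not limit that model to information known at the end of surgery.

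**What to change.** In Table 2 and the ICU row of Appendix 1:

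1. Code preoperative ICU = yes only if SCU admission precedes the Innovian surgery date, or precedes the start of surgery if times are available.
2. Define postoperative ICU separately, as a new SCU stay beginning on or after that date, or after the end of surgery if times are available.
3. For the postoperative ICU outcome, report patients already in ICU at surgery separately, or leave preoperative ICU out as a covariate. If SCU discharge dates are unavailable, apply this to all patients with preoperative ICU = yes.
4. Run the Surgical Apgar comparison also without hemoglobin and other predictors not known at the end of surgery, such as Case Mix Group.

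The cost is a wording change, a revised derivation by the data custodian, who already obtains the Innovian surgery date, and one more model comparison. SCU times or discharge dates may have to be requested. With dates only, an error remains: patients admitted to ICU on the day of surgery but before it are coded as postoperative. Their number is unknown and the limitation should be stated. Without discharge dates, patients who left ICU before surgery are also set apart for that outcome.
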